#### **6.7.2.1 Co-administration with CYP3A inhibitors**

Known strong CYP3A inhibitors (eg, itraconazole, telithromycin, clarithromycin, boosted protease inhibitors, indinavir, saquinavir, nelfinavir, boceprevir, telaprevir) or moderate CYP3A inhibitors (ciprofloxacin, erythromycin, diltiazem, fluconazole, verapamil) should not be taken with olaparib.

If there is no suitable alternative concomitant medication, then the dose of olaparib should be reduced for the period of concomitant administration. The dose reduction of olaparib should be recorded in the eCRF with the reason documented as concomitant CYP3A inhibitor use.

- Strong CYP3A inhibitors – reduce the dose of olaparib to 100 mg BID for the duration of concomitant therapy with the strong inhibitor and for 5 half-lives afterward.
- Moderate CYP3A inhibitors – reduce the dose of olaparib to 150 mg BID for the duration of concomitant therapy with the moderate inhibitor and for 3 half-lives afterward.
- After the washout of the inhibitor is complete, the olaparib dose can be re-escalated.

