**Table 7 Restricted concomitant medications**

Restricted medication/class of drug	Concern
Strong or moderate CYP3A inhibitors	Known strong CYP3A inhibitors (eg, itraconazole, telithromycin, clarithromycin, boosted protease inhibitors, indinavir, saquinavir, nelfinavir, boceprevir, telaprevir) or moderate CYP3A inhibitors (ciprofloxacin, erythromycin, diltiazem, fluconazole, verapamil) should not be taken with olaparib. If there is no suitable alternative concomitant medication, then the dose of olaparib/placebo should be reduced for the period of concomitant administration. The dose reduction of olaparib/placebo should be recorded in the eCRF with the reason documented as concomitant CYP3A inhibitor use (see Section 6.7.2).
Strong or moderate CYP3A inducers	Strong (eg, phenobarbital, phenytoin, rifampicin, rifabutin, rifapentine, carbamazepine, nevirapine, enzalutamide, and St John's Wort) and moderate CYP3A inducers (eg, bosentan, efavirenz, and modafinil) of CYP3A should not be taken with olaparib. If the use of any strong or moderate CYP3A inducers is considered necessary for the patient's safety and welfare, this could diminish the clinical efficacy of olaparib. If a patient requires use of a strong or moderate CYP3A inducer, then they must be monitored carefully for any change in efficacy of olaparib.

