### 6.7.2 Olaparib

When dose reduction is necessary, patients with  $\text{CrCl} \geq 51$  mL/min dosed with 300 mg BID will take one 150-mg tablet and one 100-mg tablet (250 mg BID) or two 100-mg tablets (200 mg BID). Patients with  $\text{CrCl} \geq 31$  mL/min but  $< 51$  mL/min dosed with 200 mg BID will take one 150-mg tablet (150 mg BID) or one 100-mg tablet (100 mg BID) (see Sections [6.7.2.1](#) and [8.4.5.2](#)). Patients

initiating olaparib at 200 mg BID due to reduced CrCl may escalate the dose to 300 mg BID at the beginning of the next treatment cycle if the CrCl increases to  $\geq 51$  mL/min. Intracycle dose escalation of olaparib is not permitted.

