#### **8.4.5 Management of IP-related toxicities and dose reductions**

The following general guidance should be followed for management of toxicities:

- Treat each of the toxicities with maximum supportive care (including holding the agent suspected of causing the toxicity if required).
- If the symptoms promptly resolve with supportive care, consideration should be given to continuing the same dose of the assigned IP along with appropriate continuing supportive care. If medically appropriate, dose modifications are permitted.
- All dose modifications should be documented with clear reasoning and documentation of the approach taken.
- Patients should be thoroughly evaluated to rule out any alternative etiology (eg, disease progression, concomitant medications, or infections).

- In the absence of a clear alternative etiology, all events should be considered potentially immune related, and the Dosing Modification and Toxicity Management Guidelines (see Section 8.4.5.1 for durvalumab and Section 8.4.5.2 for olaparib) should be followed.
- In the event that durvalumab is discontinued or delayed as part of the Dosing Modification and Toxicity Management Guidelines (Section 8.4.5), olaparib/placebo may still be administered as scheduled.
- In the event that olaparib or placebo is discontinued due to treatment-related toxicity, durvalumab may continue at the Investigator's discretion when toxicity resolves to at least Grade 2 or less. Note: If the Investigator feels that a patient is ready to restart treatment prior to the toxicity resolving to Grade 2 or less, AstraZeneca should be consulted for an exception to this rule.

If unsure how to manage a patient, please contact the Study Physician at AstraZeneca to discuss individual cases. All toxicities will be graded according to NCI CTCAE version 4.03.

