#### **8.4.5.2 Olaparib**

Any toxicity observed during the course of the study could be managed by interruption of the dose of study treatment or dose reductions. Repeat dose interruptions are allowed as required, for a maximum of 4 weeks on each occasion. If the interruption is any longer, the study team must be informed. For patients with  $\text{CrCl} \geq 51$  mL/min dosed with 300 mg BID, study treatment can be dose reduced to 250 mg BID as a first step and to 200 mg BID as a second step. If the reduced dose of 200 mg BID is not tolerable, no further dose reduction is allowed and study treatment should be discontinued.

For patients with  $\text{CrCl} \geq 31$  mL/min but  $< 51$  mL/min dosed with 200 mg BID, study treatment can be reduced to 150 mg BID as a first step and to 100 mg BID as a second step. If the reduced dose of 100 mg BID is not tolerable, no further dose reduction is allowed, and study treatment should be discontinued.

Dose re-escalation is permitted in the study at the discretion of the Investigator.

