### Interruptions for intercurrent non-toxicity-related events

Study treatment dose interruption for conditions other than toxicity resolution should be kept as short as possible. If a patient cannot restart study treatment within 4 weeks for resolution of intercurrent conditions not related to disease progression or toxicity, the case should be discussed with the AstraZeneca Study Physician.

All dose reductions and interruptions (including any missed doses) and the reasons for the reductions/interruptions are to be recorded in the eCRF.

Study treatment should be stopped at least 3 days prior to the planned surgery. After surgery, study treatment can be restarted when the wound has healed. No stoppage of study treatment is required for any needle biopsy procedure.

Study treatment should be discontinued for a minimum of 3 days before a patient undergoes radiation treatment. Study treatment should be restarted within 4 weeks as long as any bone marrow toxicity has recovered.

Because the AEs related to olaparib may include asthenia, fatigue, and dizziness, patients should be advised to use caution while driving or using machinery if these symptoms occur.

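### The fixed CYP3A-inhibitor doses in Section 6.7.2.1 give no olaparib reduction to some lower-CrCl patients already reduced for toxicity, against the section's own instruction to reduce

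*Protocol*

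**What the plan says.** Protocol Section 6.7.2.1 tells sites not to combine strong or moderate CYP3A inhibitors with olaparib. If there is no alternative, olaparib is to be lowered. Table 7 gives the same instruction: "the dose of olaparib/placebo should be reduced for the period of concomitant administration".

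Section 6.7.2.1 then sets one dose per class:
- strong inhibitor: "reduce the dose of olaparib to 100 mg BID for the duration of concomitant therapy with the strong inhibitor"
- moderate inhibitor: "reduce the dose of olaparib to 150 mg BID for the duration of concomitant therapy with the moderate inhibitor"

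Neither bullet refers to CrCl or to the dose the patient is taking.

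The doses a patient may be taking are in Table 5, Sections 6.7.2 and 8.4.5.2, and Table 14. With CrCl of at least 51 mL/min the levels are 300, 250 and 200 mg BID. With CrCl 31 to <51 mL/min the start is 200 mg BID, and Section 8.4.5.2 says "study treatment can be reduced to 150 mg BID as a first step and to 100 mg BID as a second step". The floor is explicit: "If the reduced dose of 100 mg BID is not tolerable, no further dose reduction is allowed". Section 6.7.2 cross-refers these steps to both 6.7.2.1 and 8.4.5.2. Section 6.1.1.2 supplies 100 mg and 150 mg tablets, which may not be divided.

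**The concern.** The lead-in of Section 6.7.2.1 requires a reduction, and the bullets say what to reduce to. For a lower-CrCl patient already brought down for toxicity, the named dose can equal or exceed the current one, so the two instructions cannot both be met. A site that looks up the bullet finds a definite dose and may see no reason to ask further. Olaparib then stays where it was while a drug is added that the protocol itself says calls for a cut.

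What is at stake is the safety of a small group who have both reduced renal function and earlier toxicity on olaparib. Sample size, power, alpha and the analyses are not involved.

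**Working it through.** Inputs: the two dose ladders (Sections 6.7.2 and 8.4.5.2, Table 14) and the two named doses, 150 mg BID moderate and 100 mg BID strong (Section 6.7.2.1). The plan states no figure of its own to reproduce.

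Formula: percent change = (named dose − current dose) / current dose.

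| CrCl (mL/min) | Current dose, mg BID | Moderate: to 150 | Strong: to 100 |
|---|---|---|---|
| ≥51 | 300 | −150/300 = −50% | −200/300 = −67% |
| ≥51 | 250 | −100/250 = −40% | −150/250 = −60% |
| ≥51 | 200 | −50/200 = −25% | −100/200 = −50% |
| 31 to <51 | 200 | −50/200 = −25% | −100/200 = −50% |
| 31 to <51 | 150 | 0/150 = 0% | −50/150 = −33% |
| 31 to <51 | 100 | named dose is above current; no reduction | 0/100 = 0% |

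Six dose levels by two classes give 12 cells. Nine are reduced, by 25% to 67%. These include every patient still on a starting dose and every patient with CrCl of at least 51 mL/min, whose ladder stops at 200 mg BID. The three cells with no reduction all lie in the lower-CrCl ladder after at least one toxicity step.

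The three are not equally serious:
- 150 mg BID with a moderate inhibitor: the bullet leaves the dose unchanged although 100 mg BID is an existing step. Moving there gives (100 − 150)/150 = −33%, within the 25% to 67% range of the other nine cells.
- 100 mg BID with either class: no lower dose exists, so only interruption, avoiding the inhibitor, or closer monitoring is left.
- 100 mg BID with a moderate inhibitor: this is also the dose a 150 mg BID patient would reach under the remedy proposed here, so it is a weaker example than the other two.

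**The case against.** The strongest reply is that the protocol already reaches these patients. The general instruction to reduce has no exemption by current dose. Section 6.7.2 links the 150 and 100 mg BID steps to Section 6.7.2.1, so a site that keeps 150 mg BID satisfies the bullet but not the lead-in. Section 8.4.5 offers a fallback, "If unsure how to manage a patient, please contact the Study Physician at AstraZeneca to discuss individual cases", and lists concomitant medications among the causes to rule out when toxicity occurs. Section 8.4.5.2 also allows for interruptions unrelated to toxicity: "Study treatment dose interruption for conditions other than toxicity resolution should be kept as short as possible". Inhibitors are excluded at entry with a 2-week washout (exclusion criterion 12) and are discouraged afterwards.

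Most of this stands. It means the defect is a conflict between a general sentence and a specific bullet, not a complete absence of guidance, and it keeps the point minor. It does not remove the conflict. The bullet is the more specific text, the contact route depends on the site being unsure, and neither general route deals with choosing a dose when an inhibitor is added.

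A reader might also infer that the protocol tells sites to raise a patient from 100 to 150 mg BID when a moderate inhibitor starts. That is not a reasonable reading: the verb is reduce, and Section 6.7.2 bars escalation within a cycle.

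**Conclusion.** The point holds as a minor patient-safety inconsistency. In 3 of 12 dose-by-class combinations, the dose named in Section 6.7.2.1 is not below the dose being taken, contrary to the lead-in and Table 7. The grid rests only on doses stated in the protocol.

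Few patients should be affected. The case needs CrCl 31 to <51 mL/min, an earlier toxicity reduction, and an inhibitor with no suitable alternative. Actual olaparib exposure is at issue only in the active arm, planned at 75 patients. The documents give no frequency for this combination.

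A reader might go further and infer how far exposure would rise, by assuming that the named doses restore the exposure of the starting doses. The documents do not support this. They give no exposure ratio, and the assumption contradicts itself: for a moderate inhibitor it would imply a factor of 300/150 = 2.0 for one starting dose and 200/150 = 1.33 for the other, although the rule names the same 150 mg BID for both. No size of exposure increase is therefore claimed. No statistical figure in the plan changes.

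**What to change.** In Section 6.7.2.1, with a cross-reference in Table 7, state that:
1. the named doses are maxima;
2. a patient on 150 mg BID who needs a moderate inhibitor goes to 100 mg BID;
3. for a patient already on 100 mg BID, the site contacts the Study Physician before co-administration, to choose between temporary interruption of olaparib/placebo and continuing with closer monitoring.

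Item 2 is the substantive change. Item 1 largely makes explicit what the verb and the escalation bar already imply. Item 3 largely makes an existing route explicit, and adds that contact comes before the inhibitor starts.

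The cost is two or three sentences at the next amendment. No new supply is needed, because the 100 mg tablet and the 100 mg BID step already exist. The downside is that a few patients will have a lower or interrupted olaparib dose while the inhibitor is needed and washes out.

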### **6.8 Treatment after the end of the study**

Not applicable.

## **7. DISCONTINUATION OF TREATMENT AND PATIENT WITHDRAWAL**

### **7.1 Discontinuation of study treatment**

Patients may be discontinued from the IP (durvalumab, olaparib, or placebo) if any of the following occur in the patient in question:

- Withdrawal of consent from further treatment with the IP. The patient is, at any time, free to discontinue treatment, without prejudice to further treatment. A patient who discontinues treatment is normally expected to continue to participate in the study unless they specifically withdraw their consent to further participation in any study procedures and assessments (see Section 7.3).

- An AE that, in the opinion of the Investigator or AstraZeneca, contraindicates further dosing.
- Any AE that meets criteria for discontinuation as defined in the Dosing Modification and Toxicity Management Guidelines (see Section 8.4.5.1 for durvalumab and Section 8.4.5.2 for olaparib).
- Pregnancy or intent to become pregnant.
- Non-compliance with the study protocol that, in the opinion of the Investigator or AstraZeneca, warrants withdrawal from treatment with the IP (eg, refusal to adhere to scheduled visits).
- Initiation of alternative anticancer therapy including another investigational agent.
- Clinical progression with or without RECIST 1.1-defined radiological PD. Both durvalumab and olaparib/placebo must be discontinued.
- Confirmed radiological PD ([Appendix F](#)) in clinically stable patients who were treated beyond RECIST 1.1-defined radiological PD. Both durvalumab and olaparib/placebo must be discontinued.

In the event that durvalumab is discontinued due to treatment-related toxicity, olaparib/placebo may still be administered as scheduled. If olaparib/placebo is discontinued due to treatment-related toxicity, durvalumab may continue at the Investigator's discretion when toxicity resolves to Grade 2 or less. The only circumstance where only 1 agent and not the other may be discontinued is in the event of treatment-related toxicity. Note: If the Investigator feels that a patient is ready to restart treatment prior to the toxicity resolving to Grade 2 or less, AstraZeneca should be consulted for an exception to this rule.

### **7.1.1 Procedures for discontinuation of study treatment**

Discontinuation of study treatment, for any reason, does not impact the patient's participation in the study. A patient who decides to discontinue IP will always be asked about the reason(s) for discontinuation and the presence of any AE. The patient should continue attending subsequent study visits, and data collection should continue according to the study protocol. If the patient does not agree to continue in-person study visits, a modified follow-up must be arranged to ensure the collection of endpoints and safety information. This follow-up could be a telephone contact with the patient, a contact with a relative or treating physician, or information from medical records. The approach taken should be recorded in the medical records. A patient that agrees to modified follow-up is not considered to have withdrawn consent or to have withdrawn from the study.

Patients who are permanently discontinued from further receipt of the IP, regardless of the reason, will be identified as having permanently discontinued treatment. Patients who are permanently discontinued will enter follow-up (see [Table 2](#)). Patients who permanently discontinue 1 IP due to toxicity but continue the other IP will continue all treatment assessments (see [Table 1](#)).

Patients who permanently discontinue IP for reasons other than RECIST 1.1-defined disease progression should continue to have RECIST 1.1 scans performed q8w  $\pm$ 1 week beginning 8 weeks after randomization for the first 48 weeks (relative to the date of randomization), and then every 12 weeks (q12w)  $\pm$ 1 week thereafter until clinical progression with or without RECIST 1.1-defined radiological PD plus an additional follow-up scan (if criteria for treatment beyond progression are met) or death (whichever comes first) as defined in [Table 2](#).

If a patient is discontinued for RECIST 1.1-defined progression, then the patient should have 1 additional follow-up scan performed preferably at the next (and no later than the next) scheduled imaging visit, and no less than 4 weeks after the prior assessment of PD.

All patients will be followed for survival until the end of the study.

Patients who decline to return to the site for evaluations should be contacted by telephone as indicated in [Table 2](#) as an alternative.

Patients who have permanently discontinued from further receipt of the IP will need to be discontinued from the IVRS/IWRS.

If a patient is withdrawn from study, see [Section 7.3](#).

## **7.2 Lost to follow-up**

Patients will be considered lost to follow-up only if no contact has been established by the time the study is completed (see [Section 4.3](#)), such that there is insufficient information to determine the patient's status at that time. Patients who refuse to continue participation in the study, including telephone contact, should be documented as "withdrawal of consent" rather than "lost to follow-up." Investigators should document attempts to re-establish contact with missing patients throughout the study period. Patients should be considered "potentially lost to follow-up" if contact is lost at any time during the study. If contact with a missing patient is re-established, the patient should not be considered potentially lost to follow-up, and evaluations should resume according to the protocol.

At the time of DCO, the survival status of all patients in the full analysis and the safety analysis sets should be re-checked; this includes those patients who withdrew consent or are classified as “potentially lost to follow-up.”

- Potentially lost to follow-up – site personnel should check hospital records, the patients’ current physician, and a publicly available death registry (if available) to obtain a current survival status. (The applicable eCRF modules will be updated.)
- In the event that the patient has actively withdrawn consent to the processing of their personal data, the survival status of the patient can be obtained by site personnel from publicly available death registries (if available) where it is possible to do so under applicable local laws to obtain a current survival status. (The applicable eCRF modules will be updated.)

The following actions must be taken if a patient fails to return to the clinic for a required study visit:

- The site must attempt to contact the patient and reschedule the missed visit as soon as possible and counsel the patient on the importance of maintaining the assigned visit schedule.
- Before a patient is deemed lost to follow-up, the Investigator or designee must make every effort to regain contact with the patient or next of kin by, for example, repeat telephone calls, certified letter to the patient’s last known mailing address, or local equivalent methods. These contact attempts should be documented in the patient’s medical record.
- Efforts to reach the patient should continue until the end of the study. Should the patient be unreachable at the end of the study, the patient should be considered to be lost to follow-up with unknown vital status at the end of study and censored at latest follow-up contact.

### **7.3 Withdrawal from the study**

Patients are free to withdraw from the study at any time (IP and assessments) without prejudice to further treatment.

Patients who withdraw consent for further participation in the study will not receive any further IP or further study observation, with the exception of follow-up for survival, which will continue until the end of the study unless the patient has expressly withdrawn their consent to survival follow-up. Note that the patient may be offered additional tests to withdraw safely.

A patient who withdraws consent will always be asked about the reason(s) for withdrawal and the presence of any AE. The Investigator will follow up AEs outside of the clinical study.

If a patient withdraws consent, they will be specifically asked if they are withdrawing consent to

- all further participation in the study including any further follow-up (eg, survival contact telephone calls)
- withdrawal to the use of any samples (see Section 8.8.6 withdrawal of informed consent for donated samples)

## **8. STUDY ASSESSMENTS AND PROCEDURES**

Study procedures and their timing are summarized in the SoA (Table 1).

The Web Based Data Capture (WBDC) system will be used for data collection and query handling. The Investigator will ensure that data are recorded on the eCRFs as specified in the study protocol and in accordance with the instructions provided.

The Investigator ensures the accuracy, completeness, legibility, and timeliness of the data recorded and of the provision of answers to data queries according to the Clinical Study Agreement. The Investigator will sign the completed eCRFs. A copy of the completed eCRFs will be archived at the study site.

Immediate safety concerns should be discussed with the Sponsor immediately upon occurrence or awareness to determine if the patient should continue or discontinue study treatment.

Adherence to the study design requirements, including those specified in the SoA, is essential and required for study conduct.

All screening evaluations must be completed and reviewed to confirm that potential patients meet all eligibility criteria. The Investigator will maintain a screening log to record details of all patients screened and to confirm eligibility or record reasons for screening failure, as applicable.

Procedures conducted as part of the patient's routine clinical management (eg, blood count) and obtained before signing of the ICF may be utilized for screening or baseline purposes provided the procedures met the protocol-specified criteria and were performed within the time frame defined in the SoA.

Repeat or unscheduled blood samples may be taken for safety reasons or for technical issues with the samples.

